#### Grading severity of adverse events:

The severity of AE's will be determined according to the following criteria:

Mild: Event imposes no limitations on individual's ability to perform usual activities

Moderate: Event interferes with ability to perform usual activities

Severe: Event prevents the individual from performing usual activities

#### Determining AE relatedness:

The PI will determine if an AE is "possibly related", "probably related", "definitely related", or "not related" to the study drug or a study mandated procedure. The determination will be based on the biologic plausibility, the temporal relationship, and the presence or absence of an alternative explanation for an AE. This protocol requires up to 47 months of follow up after a 14 day treatment period (with either azithromycin or placebo). Given even in the case of active drug (azithromycin), the drug will be cleared within 15 days ( $T_{1/2} = 68 \text{ hours} \times 5 = 340 \text{ hours}$  or 14.2 days), *study related* risks during the final 47 months of follow up will be from study procedures/monitoring or long term effects of prior drug exposure (e.g., a future allergic reaction). Therefore the timing of an adverse event will have a significant role in the determination of relatedness.

AEs will be categorized as having one of the following causalities:

- Not Related: The AE is clearly not related to the study drug.
- Possibly Related: The AE follows a reasonable, temporal sequence with administration of the study drug and/or follows a known response pattern to treatment with the study drug but could readily have been produced by the subject's clinical state, environmental factors, or other modes of therapy or concomitant drugs administered to the subject.
- Probably Related: The AE is uncommon in the subject population and follows a reasonable, temporal sequence from administration of study drug; follows a known response pattern to treatment with the study drug; and is not likely to have been produced by the subject's clinical state, environmental factors, or other modes of therapy or concomitant drugs administered to the subject.
- Definitely Related: The AE is uncommon in the subject population and follows a reasonable, temporal sequence from administration of study drug; follows a known response pattern to treatment with the study

drug; and cannot have been produced by the subject's clinical state, environmental factors, or other modes of therapy or concomitant drugs administered to the subject.

#### Reporting requirements:

As with all study data, AEs will be reported in a timely fashion. In all cases reporting to IRB's, NHLBI, and the FDA will be commensurate with regulatory requirements. Time sensitive reporting will be completed based on the shortest regulatory requirement of either the FDA or the IRB

#### ***Specific expedited safety reporting requirements are applicable as follows:***

- SAE, which is suspected of being related to study drug or a study mandated procedure and is unexpected (**Suspected Unexpected Serious Adverse Reaction; SUSAR**):
  - SAE that is life threatening: it must be reported to the Washington University's HRPO, the NHLBI, the FDA and DSMB within 7 working days of initial receipt of information. **If the event results in the death of a study participant, it will be reported within one working day.**
  - SAE that is non-life threatening: it must be reported to the Washington University's HRPO, the NHLBI, and the FDA and DSMB within 10 working days of initial receipt of information.
- Unanticipated problem that is not an SAE will be reported to the Washington University's HRPO, and the NHLBI within 14 working days of initial receipt of information.
- Adverse events that do not meet the definition of an unanticipated problem involving risks to participants or others will be reported to the Washington University's HRPO at the time of continuing review.
- It is expected that most study participants will have acute exacerbation of wheezing and/or asthma and some of them would require hospitalization. This is an expected outcome following hospitalization for RSV bronchiolitis, and hence does not require an expedited report.
- **Any actions issued by the WU HRPO will be reported to the NHLBI by the PI within 14 business days.**

#### Management of SAEs :

The PI or one of the other investigators, which will be designated by the PI, will decide if based on his/her best clinical judgment a SAE may be related to the study medication. If it will be determined that a SAE is possibly related, probably related, or definitely related to the study medication, then the study therapy will be discontinued. As with all AE/SAE, the participants will be followed until resolution of this event. We will not withdraw the participants from the study, as our analysis approach is an intention to treat approach.

The procedures for collection and reporting of SAEs are described above.

#### Required follow up of adverse events:

All adverse events must be followed (and documented on case report forms) until one of the following criteria is met:

- Resolution
- A documented plan for further evaluation and management, including the overseeing care provider, is provided.
- The event is considered and documented to be stable and adequately managed, though ongoing.

### C. PROTOCOL DEVIATION

- Major Protocol Deviation - A change made without prior IRB approval that has the potential to negatively impact the rights, safety, or welfare of a participant or to negatively impact the ability of a study to yield scientifically valid results.
  - Major protocol Deviation will be reported to the Washington University's HRPO within 10 working days (if the event results in death of a participant, then 1 working day).
- Minor Protocol Deviation - A change made without prior IRB approval that does not have the potential to negatively impact the rights, safety, or welfare of a participant or to negatively impact the ability of a study to yield scientifically valid results.
  - Minor protocol Deviation will be reported to the Washington University's HRPO at the time of continuing review.

### D. UNBLINDING FOR SAFETY

Treatment assignment information for each subject ID will be kept in a secure location in the St. Louis Children Hospital Pharmacy.

In the event of medical necessity, a treating physician may contact the PI (or one of the co-investigators who may cover for him) with a request for unblinding.

The PI or his designee will evaluate the request and if justified, per his/her clinical judgment, will approve the investigational pharmacist to disclose the treatment assignment to the treating physician. As much as possible, this communication regarding the actual treatment assignment should be done by the pharmacist and should not involve the PI or other research team members.

Disclosing treatment assignment would only be done in circumstances of a medical emergency in which knowing treatment assignment would impact the child's medical care. Therefore, we would not unblind if a child had an event a few months after last dose of study medication, unless there is a specific medical concern and if knowing the treatment could change patient care.

All unbinding events will be reported to the DSMB during the following DSMB meeting.

### E. CONFLICTS OF INTERESTS

All investigators identified potential Conflict of Interest (COI) by utilizing a COI Form that has been designed by the Washington University Office of Human Research. All investigators will repeat this procedure before the establishment of the research fund and then yearly.

The DSMB members will identify any potential COI at the beginning of each DSMB meeting.

## F. INTERIM ANALYSIS

An interim analysis was not specified in this protocol, as we do not believe it will serve the purpose of detecting early signal of efficacy, and it is unlikely to protect patients' safety.

This trial is design to investigate if the beneficial effects of azithromycin for the prevention of post-RSV RW, which we previously detected over one year of follow-up, are durable over the preschool years. In order to achieve this goal, this trial will include a longer follow up period (up to 48 months). Hence, interim analysis is unlikely to detect an efficacy signal and may result in false negative results.

We believe that interim analysis is unlikely to serve the purpose of protecting patients' safety, as azithromycin, which is the study intervention, is an antibiotics with a well proven safety profile, which is very commonly used in children in the clinical practice (for details see the Protection of Human Subject Section). Furthermore, the rate of adverse reactions in our pilot trial was not different between children treated with azithromycin or placebo. Nevertheless, the rate of adverse reactions will be monitored throughout the study by the investigators, the IRB, and the DSMB.

## G. STOPPING RULES

We have no stopping rules for efficacy given the potential for a false negative if the study will be stopped too early (i.e., we are not over-powered to detect the effect of the intervention).

# VII. STATISTICAL DESIGN AND ANALYSIS

## A. ANALYSIS PLAN

### General approach:

The goal of this clinical trial is to test the null hypothesis that RW is present at the same rate in the azithromycin group as compared to the placebo group. The primary analysis will be an intent-to-treat, comparing treatment groups in a Kaplan-Meier survival curves. Then, a Cox proportional hazards regression model will be used to estimate the magnitude of the treatment effect in terms of the hazard ratio for the occurrence of RW.

### Rationale for using survival analysis methodology for the primary outcome assessment:

In order to maximize the duration of follow-up in this trial which will recruit subjects over 3 consecutive RSV seasons, participants will have variable follow up durations based upon the year in which each participant will be recruited: the first season's recruits will be followed for up to 48 months, the second season will be followed up to 36 months, and the third season will be followed for at least 18 months. Maximizing the duration during which we will monitor the effect of the intervention will result in a higher likelihood of detecting the difference in outcomes between treatment groups. **Based on this study design with variable duration of follow-up, survival analysis methodology is most appropriate.**

### Primary outcome analysis:

The initial analytic strategy will be a log-rank test, which compares the Kaplan Meier survival curves describing the time to the third episode of wheezing.

Then, the primary analysis of the primary endpoint will be conducted using a stepwise Cox regression model that would include 2 covariates: race and parental history of asthma. These 2 covariates were significant predictors of childhood asthma development following severe RSV bronchiolitis in our RBEL cohort. If the proportional hazards assumption is violated, we will follow the recommendations of Allison and will address the problem by including in the model an interaction term between time and the variable that violates the proportional hazards assumption.

At the next step, we will conduct multivariate analysis that will include other covariates that may be associated with the primary outcome. Chi square tests, t-tests, and potentially Wilcoxon's test will be used to compare all non-time dependent covariates listed below\* across groups in order to identify variables that should be included in subsequent multivariate models. Those fixed-time covariates that yield at least some suggestion of a between-group difference ( $p < 0.1$ ) will then be included in a stepwise Cox regression analysis along with all of the time dependent covariates (e.g., pet exposure). Additional analyses will include the use of an Anderson-Gill model in which wheezing episodes are treated as recurrent events when compared between groups. In Cox models that do not contain time dependent covariates, we will evaluate the proportional hazards assumption by assessing the parallelism of the log-log plots and using martingale residuals and the method of Lin, and Ying. The Cox models which contain time-dependent covariates will be tested using Schoenfeld residuals.

The key statistic to be generated by the Cox regression analyses, for primary outcome reporting, will be covariate adjusted hazard rate ratios that compare the RW hazard rate in the azithromycin group with the corresponding hazard rate in the control group. Ninety-five percent confidence bounds will be generated for all calculated hazard rate ratios.

Finally, we will explore for potential interactions between study treatment assignment and pre-specified covariates to evaluate whether these covariates are predictors of response to azithromycin therapy:

- a. Demographic: Sex, age, race.
- b. Baseline asthma/allergy phenotypic characteristics: Personal history of eczema, parental history of asthma, peripheral eosinophil count on enrolment.
- c. Environmental phenotypic characteristics: second hand smoking, pet exposure.
- d. Acute bronchiolitis characteristics: Duration of respiratory symptoms before enrolment, and the presence of co-infection with other respiratory viruses during the RSV bronchiolitis (e.g. rhinovirus).

\*The following covariates will be compared between the groups and would be considered to be included in the Cox models:

- a. Age at enrollment (months)
- b. Gender
- c. Race
- d. Birth weight
- e. Length of pregnancy (wks)
- f. Maternal smoking status during pregnancy
- g. Breast feeding status at the time of enrollment

- h. Tobacco smoke exposure (at the time of enrollment and during f/u visits)
- i. Pet exposure (at the time of enrollment and during f/u visits)
- j. History of eczema
- k. Parental history of asthma
- l. Duration of respiratory symptoms prior to randomization
- m. Duration of hospitalization (hours: measured from the time of the Emergency Room visit that triggered the admission and until time of discharge)
- n. Lowest O2 saturation recorded on room air
- o. Antibiotics use during the acute hospitalization. Antibiotic use during the follow up period will be measured as one of the secondary outcomes.
- p. Co-infection with other respiratory virus on enrollment (mainly Rhinovirus)
- q. Complete compliance with study medication (defined as >80% compliance)
- r. Antipyretic (acetaminophen and Ibuprofen) use during the initial RSV bronchiolitis
- s. Day care attendance
- t. Number of siblings in the house
- u. Eosinophil count at enrollment

**Censoring considerations:** All subjects will be censored at the time of the last contact with the subject confirms that they had not experienced the outcome measure. This applies whether the subject is a dropout or has remained on study until the end.

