#### *Asthma is the most common chronic disease in childhood that carries substantial morbidity*

Approximately 7 million children under 18 years of age have a lifetime diagnosis of asthma (current asthma prevalence 9.5%). Childhood asthma exerts a significant societal burden, accounting for 5.6% of all hospitalizations in children, more than 539,000 ED visits, over 155,000 hospitalizations (more than any other chronic condition in children), 167 deaths in 2005, over 12.8 million missed school days annually, and has a total annual expenditure exceeding \$70 billion. **Asthma prevention is highly desirable, as prolonged treatment with asthma controller medications does not influence the long-term outcomes of the disease.**

Early life viral respiratory infections, particularly Respiratory Syncytial Virus (RSV) bronchiolitis, have a major role in childhood asthma inception

RSV and rhinovirus are the most common viral causes of preschool wheezing episodes, and both play major roles in asthma inception. However, the mechanisms underlying these relationships likely differ between these 2 viruses, and a causative role has been recently demonstrated between early life severe RSV infection and future RW (described below). Although most children infected with RSV experience mild disease that does not require hospitalization, RSV bronchiolitis is the leading cause of hospitalizations in infants younger than one year in the US during the winter. The occurrence of early in life severe RSV illness confers substantial risk for subsequent wheezing and asthma development, and there is a gradient of increasing risk of asthma based upon bronchiolitis severity (as reflected by level of health care utilization), with the greatest risk of asthma following bronchiolitis hospitalization.

**Figure 1.** The occurrence of recurrent wheezing and asthma following hospitalization for RSV bronchiolitis as determined in our RBEL cohort. The outcome of 3 episode of wheezing is an antecedent to asthma.

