### 1. Enrollment and Randomization visit (RZ) during the acute hospitalization:

- a. Eligibility determined based upon inclusion and exclusion criteria.
- b. Informed consent obtained.
- c. Release of medical data obtained.
- d. Provide an information brochure about the study (will include study ID, contact phone number of the investigators, instruction to avoid any macrolide antibiotic during the 2 weeks of study therapies). A copy of this brochure will be send to the primary care physician.
- e. Detailed family history and environmental allergy questionnaires obtained.
- f. Medical history obtained.
- g. Study physical examination including height and weight performed. This physical exam is performed to assure the child can participate in the study. **This exam has different goals than the physical exam performed by the child's attending physician as a standard of care, and cannot replace the attending's exam.**
- h. Document the administration over the past 24 hrs of: supplemental oxygen, IV fluids, albuterol or other bronchodilators, antibiotics.
- i. Calculate bronchiolitis severity score.
- j. Provide education about study medications, and discuss the need to avoid any macrolide antibiotic during the active phase of the study.
- k. Provide and teach Study Medication Diary (This paper diary monitor for study medications adherence and potential side effects) completion.
- l. Obtain baseline blood, stool, nasal wash and nasal brush samples, and urine (if able to obtain while child is hospitalized).
- m. Dispense first batch of study medications and dosing syringes. Teach study medication administration.
- n. Coordinate study medication delivery with the nursing staff of the inpatient unit.
- o. Schedule the clinic follow up visit (V1).
- p. Obtain contact information (including e-mail if available) and preferred time for follow up telephone calls (PCs).
- q. Provide/arrange for parent's compensation.
- r. If a Respiratory Pathogen Multiplex PCR testing has been performed in SLCH, document the presence of other respiratory viruses (if not done, this will be performed at the end of the RSV season on a nasal wash sample).

### 2. Daily follow up during the acute hospitalization (HSP1, HSP2 etc...):

- a. Review Study Medication Diary card.
- b. Review study medication treatment and adherence.

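### A bronchiolitis severity score is recorded before study drug but used in no listed analysis; pre-specifying it as a fixed covariate would cost almost nothing and could add power if it is prognostic

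*Combined protocol and SAP*

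**What the plan says.** - **Collection.** The procedures for the enrollment and randomization visit (section V.E.2, item i) include "Calculate bronchiolitis severity score". Dispensing of study medication comes later in the same list (item m), and section V.G says that drug is dispensed once data collection is complete. The score is therefore a pre-drug value.
- **Primary model.** Section VII.A, primary outcome analysis, specifies "a stepwise Cox regression model that would include 2 covariates: race and parental history of asthma". The reason given is "These 2 covariates were significant predictors of childhood asthma development following severe RSV bronchiolitis in our RBEL cohort".
- **Other covariates.** A list of 21 candidates (a to u) follows. "Those fixed-time covariates that yield at least some suggestion of a between-group difference" at p<0.1 go forward to a stepwise Cox model. Two candidates reflect severity: "Lowest O2 saturation recorded on room air" and "Duration of hospitalization (hours: measured from the time of the Emergency Room visit", the latter counted up to discharge.
- **Sensitivity analyses.** Intubation is added to the primary-outcome model if baseline covariates appear to differ between intubated and non-intubated children. The same steps are repeated for any mechanical ventilation. A LASSO selection over the fixed covariates is also planned.
- **Background.** Section II.A states that "there is a gradient of increasing risk of asthma based upon bronchiolitis severity (as reflected by level of health care utilization", with the greatest risk after hospitalization.

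The score is not named in the primary model, the treatment-interaction list, the candidate list, the sensitivity analyses, the secondary analyses or Appendix 2.

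**The concern.** A plan that measures severity on a defined instrument before treatment, and cites severity as a risk gradient for later disease, would normally use that measure or say why not. In a Cox model, leaving out a prognostic baseline variable pulls the estimated treatment hazard ratio toward 1 and costs power. The severity markers that are listed are weaker choices for baseline adjustment, because of their timing and because none enters for its prognostic value. What is at stake is some power for the primary comparison; neither validity nor type I error is in question.

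**Working it through.** **1. Where severity enters the plan**

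| Measure | Timing | How it enters |
|---|---|---|
| Severity score | Randomization visit, before drug | Not used |
| Lowest room-air oxygen saturation | No window stated | Imbalance at p<0.1, then stepwise; LASSO as sensitivity |
| Length of stay | ER visit to discharge, so partly after randomization | Same |
| Intubation; any ventilation | During the acute illness; section V.P expects that some children will worsen and need intensive care | Conditional step |

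The score is the only one of these clearly fixed at the pre-drug visit. The p<0.1 screen looks at differences between arms, not at association with wheeze, so a strongly prognostic but well-balanced marker would be left out.

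**2. Reproducing the planned sample size (section VII.B.1)**

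Inputs: monthly placebo hazards of 2% in months 1–3, rising to 5% at month 12, falling to 3% at month 24, then 2% in year 3 and 1% in year 4; two-sided 0.05; 20% dropout; 1:1 allocation; follow-up of 18–48 months over three seasons. Assumed: three equal seasons followed 42–48, 30–36 and 18–24 months, and dropout spread over 48 months.

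Placebo cumulative hazard, as the sum of −ln(1−h) with linear rise and fall: 0.061 + 0.337 + 0.480 + 0.242 + 0.121 = 1.240 (approx.). Event rate = 1 − exp(−1.240) = 71.1%, against 71.6% stated.

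Log-rank power, summed over months: Φ( |Σ(d₁ − d·p)| / √(Σ d·p(1−p)) − 1.96 ), where d is expected events, d₁ those on azithromycin, and p the azithromycin share at risk. The plan does not list monthly azithromycin hazards, so the effect pattern must be solved for:

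| Treatment hazard ratio | Power at 94 per group | Power at 70 per group |
|---|---|---|
| 0.35 to month 18, then about 1 (meets 55.1% and the other stated constraints) | 0.902 | 0.802 |
| 0.5 to month 18, 0.517 to month 24, then 1 | 0.815 | 0.693 |
| 0.5 throughout (implies 45.9% on azithromycin, not 55.1%) | 0.906 | 0.807 |

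The stated 0.90 and 0.80 therefore reproduce under the first pattern.

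**3. Adding the score**

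Simulated hazard in month m = c · h(m) · r(m)^A · exp(γZ), where h is the placebo hazard, r the treatment hazard ratio, A the arm, and Z a standard normal score. The constant c keeps the placebo event rate at its planned level. exp(γ) is the assumed hazard ratio per SD. There were 94 per arm and 2,000 trials per setting, with both Cox models fitted to the same trials. Simulation error is about 0.6 to 1.0 point per power estimate.

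| exp(γ) | Treatment effect | Power without → with score | SE of log HR |
|---|---|---|---|
| 1.0 | 0.5 constant | 0.909 → 0.905 | 0.219 → 0.219 |
| 1.2 | 0.5 constant | 0.903 → 0.914 | 0.217 → 0.218 |
| 1.5 | 0.5 constant | 0.881 → 0.906 | 0.215 → 0.216 |
| 2.0 | 0.5 constant | 0.828 → 0.920 | 0.209 → 0.212 |
| 1.0 | 0.5 to month 24, then 1 | 0.815 → 0.818 | 0.212 → 0.212 |
| 1.2 | 0.5 to month 24, then 1 | 0.808 → 0.812 | 0.211 → 0.212 |
| 1.5 | 0.5 to month 24, then 1 | 0.798 → 0.847 | 0.209 → 0.210 |
| 2.0 | 0.5 to month 24, then 1 | 0.747 → 0.875 | 0.205 → 0.207 |

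A third pattern (0.4 in months 1–12, 0.5 in 13–18, 0.65 in 19–24, then 1) gave −0.5 points at 1.0 and +0.5 at 1.1 (1,500 trials). At 1,000 trials it gave 0.855 → 0.862 at 1.3, 0.823 → 0.858 at 1.5 and 0.808 → 0.906 at 1.8.

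These comparisons start from a model with treatment alone. With two binary covariates already in the model (assumed hazard ratio 1.5 each, standing in for race and parental asthma), adding the score at 1.5 per SD took power from 0.825 to 0.872 and the SE from 0.212 to 0.214. At 1.0 per SD at most about 0.6 points were lost.

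**4. Where the gain comes from**

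At 2.0 per SD with constant effect, the mean treatment hazard ratio moves from 0.551 to 0.496:
- without the score: |ln 0.551| / 0.209 = 0.596 / 0.209 = 2.85
- with the score: |ln 0.496| / 0.212 = 0.701 / 0.212 = 3.31

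Had only the SE changed, the ratio would have fallen: 0.596 / 0.212 = 2.81. The whole gain is in the numerator.

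**The case against.** - **Premise.** A reader might infer that the protocol itself says the score predicts the outcome. It does not. The gradient in section II.A concerns asthma and ranks levels of care; every participant is hospitalized and so already at its top level. Nothing shows that the score separates hospitalized infants by risk of a third wheeze. This stands, and it is why the size of any gain is an assumption.
- **Severity is already covered.** A reader might infer that the plan ignores severity. It does not, as the first table shows. What remains is that every listed marker is screened or conditional, and that their timing is mixed or unstated.
- **Free precision.** A reader might expect a smaller standard error. In these simulations it is unchanged or rises by 0.001 to 0.003. The estimate also becomes conditional on the score, although section VII.A already makes a covariate-adjusted hazard ratio its key statistic.
- **Choice of covariates.** Race and parental asthma might be faulted because they predicted asthma and not recurrent wheeze. That would count equally against the score, which lacks even their stated support in the earlier cohort. A short pre-specified list is a legitimate choice.
- **The instrument.** Its components and scale are in a cited source. It is taken up to 7 days after symptom onset, and children weaned from ventilation may enroll, so it may miss peak severity. Linearity and overlap with oxygen saturation cannot be judged from the documents. This stands, and it makes a named sensitivity analysis an acceptable alternative.

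**Conclusion.** The point holds as a low-severity improvement: a pre-drug severity score is collected and has no stated analytic use. Adding it to a model with about 95 expected events costs one degree of freedom. Across the effect patterns tried, and allowing for simulation error, the power change at 94 per group is none at an assumed hazard ratio of 1.0 to 1.1 per SD, 0 to 2 points at 1.2, about 2.5 to 5 at 1.5 and about 8 to 10 at 1.8. The larger gains need a prognostic strength for which the documents give no evidence. The calculations also assume a normally distributed score with a log-linear effect, and treatment-effect patterns that the plan does not list month by month. The planned log-rank test and the stated sample size are unaffected, and no bias or type I error problem follows from the omission.

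**What to change.** Before unblinding:
1. In the primary outcome analysis (section VII.A), add the randomization-visit severity score as a fixed baseline covariate beside race and parental asthma, not subject to stepwise selection. If the investigators prefer the two-covariate model, define a named sensitivity analysis that adds the score.
2. Add the score to the covariate list (a to u), and state its scale, its functional form and how a missing score is handled.
3. Report the hazard ratio as conditional on the listed covariates, including the score.
4. If the score is deliberately left out, give the reason in one sentence.

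The cost is plan wording, one degree of freedom and a hazard ratio that is also conditional on the score; the data are already collected. Appendix 2 shows that covariates have already been revised during follow-up, so there is a route for the change.
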